#### 5.3 REPORTING PROCEDURES

All adverse events should be reported. Depending on the nature of the event the reporting procedures below should be followed. Any questions concerning adverse event reporting should be directed to the Chief Investigator in the first instance.

#### 5.3.1 Non serious AEs

All such events, whether expected or not, should be recorded.

#### 5.3.2 Serious AEs

An SAE form should be completed and faxed to the Chief Investigator within 24 hours. However, relapse and death due to COPD Exacerbation and hospitalisations for elective treatment of a pre-existing condition do not need reporting as SAEs.

All SAEs should be reported to the JRCO, Imperial College healthcare NHS trust where in the opinion of the Chief Investigator, the event was:

- 'related', ie resulted from the administration of any of the research procedures;
   and
- 'unexpected', ie an event that is not listed in the protocol as an expected occurrence

Reports of related and unexpected SAEs should be submitted within 15 days of the Chief Investigator becoming aware of the event, using the NRES SAE form for non-IMP studies. The Chief Investigator must also notify the Sponsor of all SAEs.

Local investigators should report any SAEs as required by their Local Research Ethics Committee, Sponsor and/or Research & Development Office.

Contact details for reporting SAEs
[contact] Attention Joint Research compliance office
Please send SAE forms to: [name]
[contact] (Mon to Fri 09.00 – 17.00)

# 6. ASSESSMENT AND FOLLOW-UP

The subjects will attend for 2 additional visits at 2 months and 3 months after completing PR for follow-up assessments that will involve completing questionnaires and measurements of exercise capacity (6 Minute Walk Test).

## **Definition of end of study**

All patients recruited to the study will have completed the study when they attend for the 3 month follow up assessments.

# 7. STATISTICS AND DATA ANALYSIS

20 patients are required in each group to detect a 30% effect size on the 6MWT with 80% power at the 5% significance level and 29 patients in each group to detect a 25% effect with 80% power. Therefore a minimum of 20 patients per group will be included. The following statistical methods will be used for data analysis – T test, ANOVA and test for correlation between variables

Data and all appropriate documentation will be stored for a minimum of 10 years after the completion of the study, including the follow-up period.

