Baseline assessments prior to commencing PR will include symptom and quality of life assessments including Borg scale for assessment of breathlessness, Chronic Respiratory Questionnaire (CRQ), COPD Assessment Tool (CAT) and the Hospital Anxiety and Depression score (HAD); a 6MWT to measure exercise capacity and Handheld dynamometer to measure muscle strength. In addition we will measure activity at home during and after PR using pedometers as this has never been investigated previously. A yamax Digi-walker SW-200 pedometer will be used to count the number of steps taken per day. Patients will be instructed to wear the device on left side of the body all the time, except when sleeping or showering. Pedometer placement was standardised by placing it on the belt or waistband, in the midline of the thigh, consistent with the manufacturers recommendation and with other studies conducted previously (6, 7). Patients will be record daily step counts on daily diary cards until their final follow up. The subjects will be randomised to receive either oxygen at the flow rate determined at the initial assessment to a maximum flow rate of 6 litres per minute, or room air. The subjects will then undergo a standard program of PR over 6 – 8 weeks and then undergo reassessment. The measures of exercise capacity at the follow up assessment will be carried out off oxygen and will be carried out by an observer blinded as to whether they received oxygen or not during PR. All patients will be provided with ambulatory oxygen for domiciliary after completing PR. All patients will have repeat assessments at 8 and 12 weeks after completion of PR. At these visits data will also be collected on activity, number of exacerbations and hospitalisations and on-going usage of ambulatory oxygen.

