#### 3.1 STUDY OUTCOME MEASURES

# **Primary Outcome measure**

Exercise capacity measured with the 6 Minute Walk Test (6MWT)

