#### 4. PARTICIPANT ENTRY

#### 4.1 PRE-REGISTRATION EVALUATIONS

6 Minute Walk Test as part of ambulatory oxygen assessment

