Appendix 1. Summary of investigations, treatment and assessments

	Baseline	PR	At completion of PR	8 weeks after PR	12 weeks after PR
6MWT	Х		X	Х	X
Borg scale	Χ		X	X	X
Chronic Respiratory Questionnaire (CRQ),	X		Х	X	х
COPD Assessment Tool (CAT)	X		X	X	х
Hospital Anxiety and Depression score (HAD)	Х		X	X	Х
Pedometer	Χ		X	X	X
Muscle strength	Х		X	X	X
Informed consent	X

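### The primary 6MWT analysis has no stated variable, visit or baseline adjustment; ANCOVA at one named visit would close the gap and add precision at almost no cost

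*Combined protocol and SAP*

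**What the plan says.** Section 7 (Statistics and Data Analysis) repeats the sample-size statement and then says: "The following statistical methods will be used for data analysis – T test, ANOVA and test for correlation between variables". It does not assign any of the three methods to an outcome, and the document nowhere mentions a covariate, ANCOVA or baseline adjustment.

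Section 3.1 gives the primary outcome as "Exercise capacity measured with the 6 Minute Walk Test (6MWT", without a derived variable or a time point.

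Section 3 lists the baseline measurements, including "a 6MWT to measure exercise capacity and Handheld dynamometer to measure muscle strength". After that, "The subjects will then undergo a standard program of PR over 6 – 8 weeks and then undergo reassessment", and "All patients will have repeat assessments at 8 and 12 weeks after completion of PR". Appendix 1 ("Summary of investigations, treatment and assessments") agrees: the 6MWT, Borg, CRQ, CAT, HAD and muscle strength are all taken at baseline, at completion of rehabilitation (PR), and 8 and 12 weeks later.

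On test conditions, Section 3 says: "The measures of exercise capacity at the follow up assessment will be carried out off oxygen". It gives no such condition for the baseline walk. Section 4.1 lists a further walk before registration: "6 Minute Walk Test as part of ambulatory oxygen assessment".

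**The concern.** A t test on follow-up distance, a t test on change from baseline and a repeated-measures ANOVA all fit Section 7. They differ in precision and can give different answers on the same data. With two variables and three visits there are six possible primary t tests, and nothing in the plan prevents the choice from being made after the results are seen.

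The trial is small (a minimum of 20 per group), and the plan does not say that randomisation is balanced on baseline 6MWD. A chance baseline difference between arms is therefore likely to be sizeable. This does not bias a randomised comparison, and the confidence interval allows for it, but it does move the estimate in the one trial that is run. On follow-up values, the baseline gap enters the estimate multiplied by the baseline to follow-up correlation ρ. On change scores it enters multiplied by (1 − ρ), in the opposite direction. ANCOVA removes it under a linear model.

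The covariate itself is also undefined. Without a statement of which baseline walk is used and under what gas condition, neither a change score nor an adjusted analysis is fully specified.

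**Working it through.** **Inputs from the documents.** Sections 3 and 7: 20 per group for a 30% effect and 29 per group for a 25% effect, 80% power, 5% significance. Sidedness, SD and the scale of the effect are not stated.

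**Assumptions.** Two-sided test; effect as a percentage of mean 6MWD; equal SD at baseline and follow-up. ρ is not in the documents and is shown at 0.5, 0.7, 0.8 and 0.9.

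**Step 1: the plan's own figures.** With a noncentral t and 80% power, the detectable standardised difference is 0.909 at 20 per arm and 0.749 at 29 per arm. The implied SD/mean is 0.30/0.909 = 0.330 and 0.25/0.749 = 0.334, so the two scenarios agree. (One-sided: 0.375 and 0.378.) Read as standardised effects of 0.30 and 0.25, the sizes would be 175 and 252 per group by normal approximation, so that reading does not fit. I use SD/mean = 0.33.

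**Step 2: SD for each analysis.**
- Follow-up values: 0.33, df 2n − 2
- Change: 0.33 × √(2(1 − ρ)), df 2n − 2
- ANCOVA: 0.33 × √(1 − ρ²), df 2n − 3

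**Step 3: results**, as % of mean 6MWD.

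| | ρ = 0.5 | 0.7 | 0.8 | 0.9 |
|---|---|---|---|---|
| Detectable at 80% power, 20 per arm: follow-up | 30.0 | 30.0 | 30.0 | 30.0 |
| change | 30.0 | 23.2 | 19.0 | 13.4 |
| ANCOVA | 26.0 | 21.4 | 18.0 | 13.1 |
| Detectable at 80% power, 29 per arm: follow-up | 24.7 | 24.7 | 24.7 | 24.7 |
| change | 24.7 | 19.1 | 15.6 | 11.0 |
| ANCOVA | 21.4 | 17.6 | 14.8 | 10.8 |
| 95% CI half-width, 20 per arm: follow-up | 21.1 | 21.1 | 21.1 | 21.1 |
| change | 21.1 | 16.4 | 13.4 | 9.4 |
| ANCOVA | 18.3 | 15.1 | 12.7 | 9.2 |

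**Step 4: ratios that do not need SD/mean or sidedness.**
- SE of ANCOVA relative to follow-up values, √(1 − ρ²): 0.87, 0.71, 0.60, 0.44. Twenty per arm then act like 20/(1 − ρ²) = 26.7, 39.2, 55.6, 105.3.
- SE of ANCOVA relative to change, √((1 + ρ)/2): 0.87, 0.92, 0.95, 0.97. Twenty per arm then act like 20 × 2/(1 + ρ) = 26.7, 23.5, 22.2, 21.1.

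**Step 5: chance baseline gap.** The SD of the gap is 0.33 × √(2/20) = 10.4% of mean 6MWD at 20 per arm, so a gap above 10% either way has probability 0.34. At 29 per arm the SD is 8.7% and the probability 0.25. A 10% gap shifts the follow-up comparison by 10ρ = 5, 7, 8, 9 points, and the change comparison by 10(1 − ρ) = 5, 3, 2, 1 points the other way.

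**Step 6: open choice of test.** Simulation with no treatment effect, 20 per arm and equal correlation among the four visits (an assumption) gives a 20 to 23% chance, for ρ from 0.5 to 0.9, that at least one of the six t tests reaches p < 0.05.

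**Step 7: cost of the covariate.** One degree of freedom. If ρ were zero, power for the 30% effect at 20 per arm would fall only from 78.1% to 78.0% (noncentral t, SD/mean 0.338).

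**The case against.** The strongest reply is that the large gains assume an unadjusted comparison of follow-up values, which the plan does not commit to. A change-score t test or repeated-measures ANOVA also fits Section 7, and both use baseline. Against change, the detectable difference improves by only about 4, 2, 1 and 0 points. That is correct. The formulas also ignore the small cost of estimating the slope when baselines differ by chance: simulation at 20 per arm puts the SE ratio against change at 0.88, 0.93, 0.96 and 0.99, so at ρ = 0.9 the gain is about 1%.

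The correlation is unknown and could be lower. At ρ = 0.3 the gain over follow-up values is slight (28.6% against 30.0%), although change scores would then do worse (35.5%). If the plan's sample sizes were worked out for change scores, the absolute percentages would shift; the SE ratios would not.

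The visit is also less open than the count of six suggests. Section 2 speaks of capacity during PR and of outcomes from it, Section 6 calls the later visits additional, and Section 3 provides ambulatory oxygen to all patients after PR. Completion of PR is strongly implied, but no section names it as primary, and the choice between follow-up value and change stays open.

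Finally, the eligibility criteria imply that a walk without oxygen took place at screening. The document does not say whether that walk is the Appendix 1 baseline.

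These points limit the size of the gain. They do not supply the missing specification.

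**Conclusion.** The concern holds. The plan states no primary 6MWT variable, no primary visit and no use of baseline, although baseline is measured for the primary outcome and for every listed secondary outcome. This does not invalidate the trial, and either t test is unbiased under randomisation. The loss is in precision and in protection against choosing the analysis afterwards.

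ANCOVA is at least as precise as either t test at every correlation examined. Its SE is 13 to 56% below that of follow-up values for ρ from 0.5 to 0.9, and about 1 to 12% below that of change scores once the slope is estimated. The ratios rest on equal SDs at the two visits. The percentages of mean distance rest also on the back-solved SD/mean of 0.33 and a two-sided test. The change should be made, and it is simple at this stage.

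**What to change.** In Section 7, specify the primary analysis as ANCOVA of 6MWD at one named visit on randomised arm, with baseline 6MWD as covariate, reporting the adjusted difference in metres with its 95% confidence interval. Completion of PR is the natural visit: it matches the aims in Section 2, and Section 3 describes the blinded, off-oxygen assessment directly after that reassessment.

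State which baseline 6MWT is the covariate and its gas condition, and use the one done under the same condition as the outcome test (off oxygen).

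Use the same model, each outcome with its own baseline, for Borg, CRQ, CAT, HAD and muscle strength. For the 8- and 12-week visits, use a baseline-adjusted mixed model with arm, visit and arm-by-visit terms and patient as the repeated unit.

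The cost is a few sentences, slightly more analysis work and one degree of freedom in the primary model. No extra patients, visits or measurements are needed.

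### Section 7 does not say how repeated visits on the same patient are analysed, and one ordinary reading of ANOVA would have a type I error of about 16% to 32%

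*Combined protocol and SAP*

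**What the plan says.** The analysis plan is one sentence in Section 7, which lists "T test, ANOVA and test for correlation between variables". It does not say whether t tests are paired, whether ANOVA is ordinary or repeated-measures, or which values enter a correlation.

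The data are repeated within patients. Section 3 sets assessments before PR, a second set after 6 to 8 weeks of PR ("and then undergo reassessment"), and two more: "All patients will have repeat assessments at 8 and 12 weeks after completion of PR". Section 6 describes the last two as "2 additional visits at 2 months and 3 months after completing PR". The table in Appendix 1 marks the 6MWT, Borg, CRQ, CAT, HAD, pedometer and muscle strength at all four occasions. Patients also "record daily step counts on daily diary cards until their final follow up", so step counts are repeated far more often. Exacerbations, hospitalisations and ongoing oxygen use are collected only at the two follow-up visits.

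Section 3.1 names the 6MWT as primary outcome without naming a visit.

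**The concern.** Values from the same patient are correlated. Of the listed methods, ANOVA is the natural one for several visits. In its ordinary two-way form (arm by visit) it has no patient term, so three or four values from one patient count as three or four patients. The standard error is then too small for the arm effect and too large for the arm-by-visit effect. A correlation that pools all visits has the first fault.

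A multi-visit analysis is foreseeable. Two of the four assessments are follow-up visits, and Section 1.1 lists short follow-up among the limitations of earlier studies. Any conclusion about the whole follow-up period, or about association between outcomes, could carry a false-positive rate several times the stated 5%. If the analyst chooses repeated-measures ANOVA instead, the cost is lost patients in a trial whose minimum is 20 per group and whose plan states no dropout allowance.

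**Working it through.** **The plan's own figure.** Section 7 gives 20 per group for a 30% effect and 29 for a 25% effect (80% power, 5% level). No SD is stated, so I solve for it, assuming a two-sided test. SD as a share of the mean = effect / [(1.960 + 0.842) × √(2/n)]:
- n = 20: 0.30 / (2.802 × 0.3162) = 0.339
- n = 29: 0.25 / (2.802 × 0.2626) = 0.340

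The two figures agree with each other and fit a two-group comparison with one value per patient. With the t distribution, 20 per group gives 80% power at 0.909 SD. That standardised effect is used below.

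**Assumptions for the rest.** Within-patient correlation ρ = 0.5 to 0.9, equal between all visits (compound symmetry); 20 per arm; two-sided 5%. The documents give no ρ.

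**Ordinary ANOVA, arm effect.** True SE / naive SE = √(1 + (m − 1)ρ) for m visits. Approximate type I error = 2 × [1 − Φ(1.96 / ratio)].

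| m | ρ | SE ratio | type I error |
|---|---|---|---|
| 3 | 0.5 | √2.0 = 1.41 | 16.6% |
| 3 | 0.9 | √2.8 = 1.67 | 24.1% |
| 4 | 0.5 | √2.5 = 1.58 | 21.5% |
| 4 | 0.9 | √3.7 = 1.92 | 30.8% |

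Simulations under the null agree: about 16% to 25% with 3 visits and 22% to 32% with 4.

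**Ordinary ANOVA, arm by visit.** The true variance of this contrast is proportional to 1 − ρ, but the residual mean square estimates the full variance. The naive SE is too large by 1/√(1 − ρ), which is 1.41 at ρ = 0.5 and 3.16 at ρ = 0.9. Simulated rejection under the null is 0% to 0.4%.

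**Pooled correlation, 40 patients.** For two unrelated outcomes with the same ρ, the variance of the coefficient is inflated by about 1 + (m − 1)ρ².
- m = 2 (for example oxygen use): factor 1.25 to 1.81, type I error about 8% to 15%; simulated about 8% to 16%.
- m = 4: factor 1.75 to 3.43, type I error about 14% to 29%; simulated about 13% to 30%.

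**Uses of the named tests that are valid.** Simulated type I error is 4.8% to 5.2% for a between-arm t test at one visit, 4.9% to 5.2% for a t test on change scores, and 4.9% to 5.3% for a paired t test within an arm.

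**Repeated-measures ANOVA.** Error is controlled, but a patient needs every visit. With a proportion q of values missing independently at each of 3 visits (assumed), 20 × (1 − q)³ patients remain per arm: 17.1, 14.6 and 12.3 for q = 5%, 10% and 15%. The between-arm test uses the patient mean, so a constant 0.909 SD effect becomes 0.909 / √((1 + 2ρ)/3), that is 1.113 at ρ = 0.5 and 0.941 at ρ = 0.9.

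| patients per arm | power, ρ = 0.9 to 0.5 |
|---|---|
| 20 | 83% to 93% |
| 17 | 76% to 88% |
| 15 | 70% to 84% |
| 12 | 60% to 74% |

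**The case against.** The strongest reply is that the plan nowhere says visits will be pooled as independent. A t test may be paired, ANOVA may be repeated-measures, and the sample size fits one value per patient. This stands. A reader might infer that the planned standard errors are wrong as written; the documents do not support that. A comparison at a single visit has no repeated-measures problem at all.

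Three other inferences also go too far:
- That every outcome is measured four times. Oxygen use, exacerbations and hospitalisations are collected at two visits, so a pooled correlation with oxygen use carries about 8% to 16% error, not the four-visit rate.
- That missed visits cut power from 80% to 73%, 67% or 57%. Those are the powers of a single-visit t test with 17, 15 and 12 per arm. Repeated-measures ANOVA has the higher values shown in the last table.
- That a changing effect could not be detected. The near-zero figure is a rejection rate under the null; power against a time-varying effect was not calculated.

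The reply does not close the gap. The same sentence permits a test with about 5% error and one with up to 32%, and nothing elsewhere in the document chooses between them.

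**Conclusion.** The point holds as an unspecified method with a foreseeable invalid reading, not as a demonstrated error. The primary comparison is sound if it is made at one visit or on change from baseline. It is unsound if ANOVA is run across visits without a patient term. The conservative reading, repeated-measures ANOVA, is valid but loses patients.

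The sizes rest on assumed values: ρ of 0.5 to 0.9, compound symmetry, and 5% to 15% of values missing independently at each visit. A lower ρ would shrink the excess type I error. Missed visits that cluster in the same patients, as with permanent dropout, would leave more complete cases than shown for the same per-visit rate. The direction of each error does not depend on the exact values.

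**What to change.** In Section 7, for outcomes measured at several visits, replace ANOVA with a linear mixed model: arm, visit and arm-by-visit as fixed effects; a within-patient covariance (unstructured, or a patient random effect); small-sample degrees of freedom such as Kenward–Roger; all available visits used. Take the arm contrast at each visit from this model. State whether baseline enters as a visit or as a covariate.

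Limit t tests to one value per patient (a single visit or a change score), and limit correlations likewise, for example to the change from baseline to completion of PR.

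The mixed model keeps patients who miss a visit, under the usual assumption that values are missing at random; Section 7 should state that assumption. A baseline-adjusted comparison at one named visit would also be valid for that visit, but would not cover the follow-up period. The cost is a few lines of text and slightly more analysis work, with no new data or visits.

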# 8. REGULATORY ISSUES

#### 8.1 ETHICS APPROVAL

The Chief Investigator has obtained approval from the Local Research Ethics Committee. The study must be submitted for Site Specific Assessment (SSA) at each participating NHS Trust. The Chief Investigator will require a copy of the Trust R&D approval letter before accepting participants into the study. The study will be conducted in accordance with the recommendations for physicians involved in research on human subjects adopted by the 18th World Medical Assembly, Helsinki 1964 and later revisions.

#### 8.2 CONSENT

Consent to enter the study must be sought from each participant only after a full explanation has been given, an information leaflet offered and time allowed for consideration. Signed participant consent should be obtained. The right of the participant to refuse to participate without giving reasons must be respected. After the participant has entered the study the clinician remains free to give alternative treatment to that specified in the protocol at any stage if he/she feels it is in the participant's best interest, but the reasons for doing so should be

recorded. In these cases the participants remain within the study for the purposes of followup and data analysis. All participants are free to withdraw at any time from the protocol treatment without giving reasons and without prejudicing further treatment.

#### 8.3 CONFIDENTIALITY

The Chief Investigator will preserve the confidentiality of participants taking part in the study and is registered under the Data Protection Act.

#### 8.4 INDEMNITY

Imperial College Healthcare NHS Trust holds standard NHS Hospital Indemnity and insurance cover with NHS Litigation Authority for NHS Trusts in England, which apply to this study

#### 8.5 SPONSOR

Imperial College Healthcare NHS Trust will act as the main Sponsor for this study. Delegated responsibilities will be assigned to the NHS trusts taking part in this study.

#### 8.6 FUNDING

NIHR Imperial BRC is funding this study. Total of 50000£ for a year, has been awarded to the chief investigator as part of the Research fellowship

#### 8.7 AUDITS

The study may be subject to inspection and audit by Imperial College healthcare NHS trust under their remit as sponsor and other regulatory bodies to ensure adherence to GCP and the NHS Research Governance Framework for Health and Social Care (2nd edition).

## 9. STUDY MANAGEMENT

The day-to-day management of the study will be co-ordinated by the chief investigator

